## Interim analysis

None planned.

## Analysis of subgroups

Subgroup analysis will be planned and executed after unblinding, if their distribution of demographic groups across trial arms allows for it.

## Source code

Supplementary file 1 is provided at the end of this SAP, representing the source code for statistical analysis using R. Ideally, this code should not be changed after unblinding. Still, due to discrepancies between databases before and after unblinding, minimal adjustments to the statistical routines (especially for data loading) might be required. All subsequent source code changes should be documented, and the final source code version used in statistical analysis should be made available together with the CSR.

## Planned tables and graphs

### Planned tables

- table1demographics.xlsx: demographics and baseline characteristics of each group; this table will also contain the results of the statistical tests done for comparability between groups
- 
- itt/3dWABAQ.xlsx: WAB Aphasia Quotient differentials at visits 2/3/4, comparisons with baseline and comparisons of differentials between groups, at each visit
- itt/4dNIHSST.xlsx: NIHSS differentials at visits 2/3/4, comparisons with baseline and comparisons of differentials between groups, at each visit
- itt/5BIT.xlsx: Barthel Index scores at visits 2/3/4, comparisons of differentials from visits 3/4 against visit 2, and comparisons of those differentials between groups, at visits 3/4
- itt/6MRS.xlsx: modified Rankin Score at visits 2/3/4, comparisons of differentials from visits 3/4 against visit 2, and comparisons of those differentials between groups, at visits 3/4
- pp/3dWABAQ.xlsx: WAB Aphasia Quotient differentials at visits 2/3/4, comparisons with baseline and comparisons of differentials between groups, at each visit
- pp/4dNIHSST.xlsx: NIHSS differentials at visits 2/3/4, comparisons with baseline and comparisons of differentials between groups, at each visit

- pp/5BIT.xlsx: Barthel Index scores at visits 2/3/4, comparisons of differentials from visits 3/4 against visit 2, and comparisons of those differentials between groups, at visits 3/4
- pp/6MRS.xlsx: modified Rankin Score at visits 2/3/4, comparisons of differentials from visits 3/4 against visit 2, and comparisons of those differentials between groups, at visits 3/4
- AE\_table.xlsx: counting of total AEs, SAEs and specific AE categories, as well as statistical tests between groups.

## Planned graphs

- itt/1WABAQ.png: Boxplot showing the WAB aphasia quotient score (Oy) for each group (fill) at each visit (1/2/3/4) (Ox)
- itt/2NIHSST.png: Boxplot showing the NIHSS score (Oy) for each group (fill) at each visit (1/2/3/4) (Ox)
- itt/3dWABAQ.png: Boxplot showing the WAB aphasia quotient differential (Oy) for each group (fill) at each visit (2/3/4 compared to 1) (Ox)
- 4dNIHSST.png: Boxplot showing the NIHSS score differential (Oy) for each group (fill) at each visit (2/3/4 compared to 1) (Ox)
- itt/5BIT.png and itt/6MRS.png: Boxplot showing the respective score (Oy) for each group (fill) at each visit (2/3/4)
- pp/1\* to 6\*: the same graphs, redone for the Per Protocol analysis set
- AE\_number\_of\_AEs.png: barplot showing the total number (Oy) of AEs, SAEs and specific categories (Ox) by group (fill)
- AE\_number\_of\_patients.png: barplot showing the total number of patients (Oy) accusing AEs, SAEs or specific categories (Ox) by group (fill)
- AE\_percent\_of\_patients.png: barplot showing the percentage of patients (Oy) accusing AEs, SAEs and specific categories (Ox) by group (fill)

## Supplementary file: R source code

```
# ESCAS statistical analysis code
# Author: [name], [contact]
library(readxl)
library(xlsx)
library(stringr)
library(ggplot2)
#library(MANOVA.RM)
# Some general functions ----
beautiful.p.value<-function(x){ #beautiful p value, if strictly under 0.001 print as <0.001,
otherwise print as =0.***
  x<-as.numeric(x)
  if(is.na(x))
    return("NA")
```

```
if(is.nan(x))
  return("NaN")
if(x<0.001)
  return("<0.001")
return(paste("",round(x,3),sep=""))
}
test.numeric.unpaired<-function(t1,t2){
  ret<-list()
  ret$sum_nas<-sum(is.na(t1))+sum(is.na(t2))
  t1<-t1[!is.na(t1)]
  t2<-t2[!is.na(t2)]
  if(length(unique(t1))==1)
    ret$shapiro.p.t1<-1
  else
    ret$shapiro.p.t1<-shapiro.test(t1)$p.value
  if(length(unique(t2))==1)
    ret$shapiro.p.t2<-1
  else
    ret$shapiro.p.t2<-shapiro.test(t2)$p.value
  if(ret$shapiro.p.t1<0.05|ret$shapiro.p.t2<0.05){ # if any of them is not normally distributed
    ret$final.test<-"Wilcoxon rank sum"
    ret$p.value<-wilcox.test(t1,t2,paired = F)$p.value
  }else{
    ret$bartlett.p<-bartlett.test(list(t1,t2))$p.value
    if(ret$bartlett.p<0.05){ # unequal distrib
      ret$final.test<-"Student T test for unpaired samples and unequal variances"
      ret$p.value<-t.test(t1,t2,paired = F,var.equal = F)$p.value
    }else{
      ret$final.test<-"Student T test for unpaired samples and equal variances"
      ret$p.value<-t.test(t1,t2,paired = F,var.equal = T)$p.value
    }
  }
  return(ret)
}
test.numeric.paired.2<-function(t1,t2){
  ret<-list()
  if(length(t1)!=length(t2))
    stop("Different lengths!")
  ret$na_vals<-is.na(t1)|is.na(t2)
  t1<-t1[!ret$na_vals]
  t2<-t2[!ret$na_vals]
  ret$shapiro.p.t1<-shapiro.test(t1)$p.value
  ret$shapiro.p.t2<-shapiro.test(t2)$p.value
  if(ret$shapiro.p.t1<0.05|ret$shapiro.p.t2<0.05){ # if any of them is not normally distributed
```

```

ret$final.test<-"Wilcoxon signed rank"
ret$p.value<-wilcox.test(t1,t2,paired = T)$p.value
}else{
ret$final.test<-"Student T test for paired samples"
ret$p.value<-t.test(t1,t2,paired = T)$p.value
}
return(ret)
}
test.numeric.paired.1<-function(tx){ #the same idea, but for when I supply only one group of
values
ret<-list()
ret$na_vals<-is.na(tx)
tx<-tx[!ret$na_vals]
ret$shapiro.p<-shapiro.test(tx)$p.value
if(ret$shapiro.p<0.05){
ret$final.test<-"Wilcoxon signed rank"
ret$p.value<-wilcox.test(tx)$p.value
}else{
ret$final.test<-"Student T test for one sample"
ret$p.value<-t.test(tx)$p.value
}
return(ret)
}
contingency.table.test<-function(t){
if(nrow(t)==2 & ncol(t)==2){
f<-fisher.test(t)
bigtotal<-sum(t)
can_use_chisq<-
(sum(t[1,])*sum(t[,1])/bigtotal>=5) &
(sum(t[1,])*sum(t[,2])/bigtotal>=5) &
(sum(t[2,])*sum(t[,1])/bigtotal>=5) &
(sum(t[2,])*sum(t[,2])/bigtotal>=5)
ret<-c(
"p_chi2_cor"=chisq.test(t)$p.value,
"p_chi2"=chisq.test(t,correct = F)$p.value,
"p_fisher"=f$p.value,
"p_chosen"=ifelse(can_use_chisq,chisq.test(t,correct = F)$p.value,f$p.value),
"can_use_chi2"=can_use_chisq,
"OR"=t[1,1]*t[2,2]/(t[1,2]*t[2,1]),
"OR_inf"=exp(log(t[1,1]*t[2,2]/(t[1,2]*t[2,1]))-1.96*sqrt(1/t[1,1]+1/t[1,2]+1/t[2,1]+1/t[2,2])),
"OR_sup"=exp(log(t[1,1]*t[2,2]/(t[1,2]*t[2,1]))+1.96*sqrt(1/t[1,1]+1/t[1,2]+1/t[2,1]+1/t[2,2])),
"OR_Fisher"=unname(f$estimate),
"OR_F_inf"=f$conf.int[1],
"OR_F_sup"=f$conf.int[2],

```

```

"shorthand"=paste(
  ifelse(can_use_chisq,"Chi2","Fisher")," ",
  beautiful.p.value(ifelse(can_use_chisq,chisq.test(t,correct = F)$p.value,f$p.value)),
  " OR=",
  round(t[1,1]*t[2,2]/(t[1,2]*t[2,1]),3),
  sep=""
)
)
ret
}
else
{
f<-fisher.test(t)
y<-0
for(j in 1:nrow(t))
  for(k in 1:ncol(t))
    y<-y+(sum(t[j,])*sum(t[,k])/sum(t))>=5)
can_use_chisq<-(y/(nrow(t)*ncol(t))>=0.8)
ret<-c(
  "p_chi2_cor"=chisq.test(t)$p.value,
  "p_chi2"=chisq.test(t,correct = F)$p.value,
  "p_fisher"=fisher.test(t)$p.value,
  "p_chosen"=ifelse(can_use_chisq,chisq.test(t,correct = F)$p.value,fisher.test(t)$p.value),
  "can_use_chi2"=can_use_chisq,
  "shorthand"=paste(
    ifelse(can_use_chisq,"Chi2","Fisher")," ",
    beautiful.p.value(ifelse(can_use_chisq,chisq.test(t,correct = F)$p.value,f$p.value)),
    sep=""
  )
)
ret
}
}
descr.numeric.meansd<-function(x){
  return(paste0(round(mean(x),3),"±",round(sd(x),3)))
}
descr.numeric.median<-function(x){
  x<-quantile(x)
  return(paste0(round(x[3],3)," (",round(x[2],3)," - ",round(x[4],3),")"))
}
# Load data - this might change ----
db_scores<-data.frame(read_excel("dbfin.xlsx","only_total_scores"))
db_bigdat<-data.frame(read_excel("dbfin.xlsx","escas_data"))
db_assign<-data.frame(read_excel("rndtest.xlsx"))

```

```

db_advers<-data.frame(read_excel("dbfin.xlsx","adverse_events"))
names(db_assign)<-c("RDMNUM","is_crb","is_pp")
# NB: rndtest is a database for test, which contains the group assignment data (RDMNUM,
is_crb and is_pp)
# this portion of code is subject to changes after unblinding to adapt the unblinding data format
to preexistent code
## Check uniqueness of the RDMNUM just for sanity ----
t1<-table(db_scores$RDMNUM)
t2<-table(db_bigdat$RDMNUM)
t3<-table(db_assign$RDMNUM)
sum(!t1==1)
sum(!t2==1)
sum(!t3==1)
sum(names(t1)!=names(t2))
sum(names(t1)!=names(t3))
## Introduce grouping and population info into the data frames ----
for(i in 1:nrow(db_scores)){
  db_scores[i,"is_crb"]<-db_assign[db_assign$RDMNUM==db_scores$RDMNUM[i],"is_crb"]
  db_bigdat[i,"is_crb"]<-db_assign[db_assign$RDMNUM==db_bigdat$RDMNUM[i],"is_crb"]
  db_scores[i,"is_pp"]<-db_assign[db_assign$RDMNUM==db_scores$RDMNUM[i],"is_pp"]
  db_bigdat[i,"is_pp"]<-db_assign[db_assign$RDMNUM==db_bigdat$RDMNUM[i],"is_pp"]
}
# TABLE 1 DEMOGRAPHICS ----
beautiful_table<-data.frame(
  Characteristic=as.character(),
  Variant=as.character(),
  CRB=as.character(),
  PLC=as.character(),
  p.value=as.character(),
  test=as.character()
)
## Number of patients in each group ----
beautiful_table[1,]<-c(
  "N=",
  "",
  paste0(sum(db_assign$is_crb),"
(",round(sum(db_assign$is_crb)/nrow(db_assign)*100,3,"%)" ),
  paste0(sum(!db_assign$is_crb),"
(",round(sum(!db_assign$is_crb)/nrow(db_assign)*100,3,"%)" ),
  "", ""
)
## Age ----
db_bigdat$computed_age<-floor(as.numeric((db_bigdat$SODTC-db_bigdat$BIRTHDT)/365.25))
x<-test.numeric.unpaired(

```

```

(db_bigdat$computed_age[db_bigdat$sis_crb]),
(db_bigdat$computed_age[!db_bigdat$sis_crb])
)
beautiful_table[2,]<-c(
  "Age","mean+sd",
  descr.numeric.meansd(db_bigdat$computed_age[db_bigdat$sis_crb]),
  descr.numeric.meansd(db_bigdat$computed_age[!db_bigdat$sis_crb]),
  beautiful.p.value(x$p.value),x$final.test
)
beautiful_table[3,]<-c(
  "", "median",
  descr.numeric.median(db_bigdat$computed_age[db_bigdat$sis_crb]),
  descr.numeric.median(db_bigdat$computed_age[!db_bigdat$sis_crb]),
  "", ""
)
)
## Sex ----
x<-contingency.table.test(table(db_bigdat$SEX,db_bigdat$sis_crb))
beautiful_table[4,]<-c(
  "Sex","Female",
  paste0(sum(db_bigdat$SEX==2&db_bigdat$sis_crb),"
(",round(sum(db_bigdat$SEX==2&db_bigdat$sis_crb)/sum(db_bigdat$sis_crb)*100,3),"%")),
  paste0(sum(db_bigdat$SEX==2&!db_bigdat$sis_crb),"
(",round(sum(db_bigdat$SEX==2&!db_bigdat$sis_crb)/sum(!db_bigdat$sis_crb)*100,3),"%")),
  beautiful.p.value((x[["p_chosen"]]),ifelse(x[["can_use_chi2"]]=="TRUE","Chi^2 test","Fisher test"))
)
beautiful_table[5,]<-c(
  "", "Male",
  paste0(sum(db_bigdat$SEX==1&db_bigdat$sis_crb),"
(",round(sum(db_bigdat$SEX==1&db_bigdat$sis_crb)/sum(db_bigdat$sis_crb)*100,3),"%")),
  paste0(sum(db_bigdat$SEX==1&!db_bigdat$sis_crb),"
(",round(sum(db_bigdat$SEX==1&!db_bigdat$sis_crb)/sum(!db_bigdat$sis_crb)*100,3),"%")),
  "", ""
)
)

## Education level ----
x<-contingency.table.test(table(db_bigdat$EDU,db_bigdat$sis_crb))
beautiful_table[6,]<-c(
  "Education","No formal education",
  paste0(sum(db_bigdat$EDU==1&db_bigdat$sis_crb),"
(",round(sum(db_bigdat$EDU==1&db_bigdat$sis_crb)/sum(db_bigdat$sis_crb)*100,3),"%")),
  paste0(sum(db_bigdat$EDU==1&!db_bigdat$sis_crb),"
(",round(sum(db_bigdat$EDU==1&!db_bigdat$sis_crb)/sum(!db_bigdat$sis_crb)*100,3),"%")),
  beautiful.p.value((x[["p_chosen"]]),ifelse(x[["can_use_chi2"]]=="TRUE","Chi^2 test","Fisher test"))
)
)

```

```

beautiful_table[7,]<-c(
  "", "Primary school",
  paste0(sum(db_bigdat$EDU==2&db_bigdat$is_crb),
  ("round(sum(db_bigdat$EDU==2&db_bigdat$is_crb)/sum(db_bigdat$is_crb)*100,3,"%")),
  paste0(sum(db_bigdat$EDU==2&!db_bigdat$is_crb)),
  ("round(sum(db_bigdat$EDU==2&!db_bigdat$is_crb))/sum(!db_bigdat$is_crb)*100,3,"%")),
  "", ""
)
beautiful_table[8,]<-c(
  "", "Secondary school",
  paste0(sum(db_bigdat$EDU==3&db_bigdat$is_crb),
  ("round(sum(db_bigdat$EDU==3&db_bigdat$is_crb)/sum(db_bigdat$is_crb)*100,3,"%")),
  paste0(sum(db_bigdat$EDU==3&!db_bigdat$is_crb)),
  ("round(sum(db_bigdat$EDU==3&!db_bigdat$is_crb))/sum(!db_bigdat$is_crb)*100,3,"%")),
  "", ""
)
beautiful_table[9,]<-c(
  "", "High school",
  paste0(sum(db_bigdat$EDU==4&db_bigdat$is_crb),
  ("round(sum(db_bigdat$EDU==4&db_bigdat$is_crb)/sum(db_bigdat$is_crb)*100,3,"%")),
  paste0(sum(db_bigdat$EDU==4&!db_bigdat$is_crb)),
  ("round(sum(db_bigdat$EDU==4&!db_bigdat$is_crb))/sum(!db_bigdat$is_crb)*100,3,"%")),
  "", ""
)
beautiful_table[10,]<-c(
  "", "University",
  paste0(sum(db_bigdat$EDU==5&db_bigdat$is_crb),
  ("round(sum(db_bigdat$EDU==5&db_bigdat$is_crb)/sum(db_bigdat$is_crb)*100,3,"%")),
  paste0(sum(db_bigdat$EDU==5&!db_bigdat$is_crb)),
  ("round(sum(db_bigdat$EDU==5&!db_bigdat$is_crb))/sum(!db_bigdat$is_crb)*100,3,"%")),
  "", ""
)
x<-
test.numeric.unpaired(db_bigdat$EDU[db_bigdat$is_crb],db_bigdat$EDU[!db_bigdat$is_crb])
beautiful_table[11,]<-c(
  "", "treat as numbers",
  descr.numeric.median(db_bigdat$EDU[db_bigdat$is_crb]),
  descr.numeric.median(db_bigdat$EDU[!db_bigdat$is_crb]),
  beautiful.p.value(x$p.value),x$final.test
)

## Writing hand ----
x<-contingency.table.test(table(db_bigdat$WHRES,db_bigdat$is_crb))
beautiful_table[12,]<-c(

```

```

"Writing hand","Right",
paste0(sum(db_bigdat$WHRES==2&db_bigdat$sis_crb),"
(",round(sum(db_bigdat$WHRES==2&db_bigdat$sis_crb)/sum(db_bigdat$sis_crb)*100,3),"%"),
paste0(sum(db_bigdat$WHRES==2&(!db_bigdat$sis_crb)),
(",round(sum(db_bigdat$WHRES==2&(!db_bigdat$sis_crb))/sum(!db_bigdat$sis_crb)*100,3),"%")
),
beautiful.p.value((x[["p_chosen"]]),ifelse(x[["can_use_chi2"]=="TRUE","Chi^2 test","Fisher test")
)
beautiful_table[13,]<-c(
"", "Left",
paste0(sum(db_bigdat$WHRES==1&db_bigdat$sis_crb),"
(",round(sum(db_bigdat$WHRES==1&db_bigdat$sis_crb)/sum(db_bigdat$sis_crb)*100,3),"%"),
paste0(sum(db_bigdat$WHRES==1&(!db_bigdat$sis_crb)),
(",round(sum(db_bigdat$WHRES==1&(!db_bigdat$sis_crb))/sum(!db_bigdat$sis_crb)*100,3),"%")
),
"", ""
)
## Alcohol ----
x<-contingency.table.test(table(db_bigdat$Substances_alcohol,db_bigdat$sis_crb))
beautiful_table[14,]<-c(
"Alcohol use","None",
paste0(sum(db_bigdat$Substances_alcohol==1&db_bigdat$sis_crb),"
(",round(sum(db_bigdat$Substances_alcohol==1&db_bigdat$sis_crb)/sum(db_bigdat$sis_crb)*100,3),"%"),
paste0(sum(db_bigdat$Substances_alcohol==1&(!db_bigdat$sis_crb)),
(",round(sum(db_bigdat$Substances_alcohol==1&(!db_bigdat$sis_crb))/sum(!db_bigdat$sis_crb)*100,3),"%"),
beautiful.p.value((x[["p_chosen"]]),ifelse(x[["can_use_chi2"]=="TRUE","Chi^2 test","Fisher test")
)
beautiful_table[15,]<-c(
"", "Use",
paste0(sum(db_bigdat$Substances_alcohol==2&db_bigdat$sis_crb),"
(",round(sum(db_bigdat$Substances_alcohol==2&db_bigdat$sis_crb)/sum(db_bigdat$sis_crb)*100,3),"%"),
paste0(sum(db_bigdat$Substances_alcohol==2&(!db_bigdat$sis_crb)),
(",round(sum(db_bigdat$Substances_alcohol==2&(!db_bigdat$sis_crb))/sum(!db_bigdat$sis_crb)*100,3),"%"),
"", ""
)
beautiful_table[16,]<-c(
"", "Abuse",
paste0(sum(db_bigdat$Substances_alcohol==3&db_bigdat$sis_crb),"
(",round(sum(db_bigdat$Substances_alcohol==3&db_bigdat$sis_crb)/sum(db_bigdat$sis_crb)*100,3),"%"),

```

```
paste0(sum(db_bigdat$Substances_alcohol==3&!db_bigdat$sis_crb)),"
(",round(sum(db_bigdat$Substances_alcohol==3&!db_bigdat$sis_crb))/sum(!db_bigdat$sis_crb)*
100,3,"%"),
"", ""
)
x<-
test.numeric.unpaired(db_bigdat$Substances_alcohol[db_bigdat$sis_crb],db_bigdat$Substances
_alcohol[!db_bigdat$sis_crb])
beautiful_table[17,]<-c(
  "", "treat as numbers",
  descr.numeric.median(db_bigdat$Substances_alcohol[db_bigdat$sis_crb]),
  descr.numeric.median(db_bigdat$Substances_alcohol[!db_bigdat$sis_crb]),
  beautiful.p.value(x$p.value),x$final.test
)
### Other substances ----
x<-contingency.table.test(table(db_bigdat$Substances_other,db_bigdat$sis_crb))
beautiful_table[18,]<-c(
  "Other substances use","None",
  paste0(sum(db_bigdat$Substances_other==1&db_bigdat$sis_crb),"
(",round(sum(db_bigdat$Substances_other==1&db_bigdat$sis_crb)/sum(db_bigdat$sis_crb)*100,
3,"%"),
  paste0(sum(db_bigdat$Substances_other==1&!db_bigdat$sis_crb),"
(",round(sum(db_bigdat$Substances_other==1&!db_bigdat$sis_crb))/sum(!db_bigdat$sis_crb)*1
00,3,"%"),
  beautiful.p.value((x[["p_chosen"]]),ifelse(x[["can_use_chi2"]=="TRUE","Chi^2 test","Fisher test")
)
beautiful_table[19,]<-c(
  "", "Use",
  paste0(sum(db_bigdat$Substances_other==2&db_bigdat$sis_crb),"
(",round(sum(db_bigdat$Substances_other==2&db_bigdat$sis_crb)/sum(db_bigdat$sis_crb)*100,
3,"%"),
  paste0(sum(db_bigdat$Substances_other==2&!db_bigdat$sis_crb),"
(",round(sum(db_bigdat$Substances_other==2&!db_bigdat$sis_crb))/sum(!db_bigdat$sis_crb)*1
00,3,"%"),
  "", ""
)
beautiful_table[20,]<-c(
  "", "Abuse",
  paste0(sum(db_bigdat$Substances_other==3&db_bigdat$sis_crb),"
(",round(sum(db_bigdat$Substances_other==3&db_bigdat$sis_crb)/sum(db_bigdat$sis_crb)*100,
3,"%"),
  paste0(sum(db_bigdat$Substances_other==3&!db_bigdat$sis_crb),"
(",round(sum(db_bigdat$Substances_other==3&!db_bigdat$sis_crb))/sum(!db_bigdat$sis_crb)*1
00,3,"%"),
```

```
    "" , ""
  )
x<-
test.numeric.unpaired(db_bigdat$Substances_other[db_bigdat$sis_crb],db_bigdat$Substances_
other[!db_bigdat$sis_crb])
beautiful_table[21,]<-c(
  "" , "treat as numbers",
  descr.numeric.median(db_bigdat$Substances_other[db_bigdat$sis_crb]),
  descr.numeric.median(db_bigdat$Substances_other[!db_bigdat$sis_crb]),
  beautiful.p.value(x$p.value),x$final.test
)
## WAB Aphasia quotient ----
x<-
test.numeric.unpaired(db_bigdat$WABAQ_1[db_bigdat$sis_crb],db_bigdat$WABAQ_1[!db_bigd
at$sis_crb])
beautiful_table[22,]<-c(
  "WAB Aphasia quotient", "mean+sd",
  descr.numeric.meansd(db_bigdat$WABAQ_1[db_bigdat$sis_crb]),
  descr.numeric.meansd(db_bigdat$WABAQ_1[!db_bigdat$sis_crb]),
  beautiful.p.value(x$p.value),x$final.test
)
beautiful_table[23,]<-c(
  "" , "median",
  descr.numeric.median(db_bigdat$WABAQ_1[db_bigdat$sis_crb]),
  descr.numeric.median(db_bigdat$WABAQ_1[!db_bigdat$sis_crb]),
  "" , ""
)
## NIHSS ----
x<-
test.numeric.unpaired(db_bigdat$NIHSST_1[db_bigdat$sis_crb],db_bigdat$NIHSST_1[!db_bigda
t$sis_crb])
beautiful_table[24,]<-c(
  "NIHSS", "mean+sd",
  descr.numeric.meansd(db_bigdat$NIHSST_1[db_bigdat$sis_crb]),
  descr.numeric.meansd(db_bigdat$NIHSST_1[!db_bigdat$sis_crb]),
  beautiful.p.value(x$p.value),x$final.test
)
beautiful_table[25,]<-c(
  "" , "median",
  descr.numeric.median(db_bigdat$NIHSST_1[db_bigdat$sis_crb]),
  descr.numeric.median(db_bigdat$NIHSST_1[!db_bigdat$sis_crb]),
  "" , ""
)
write.xlsx(beautiful_table,"table1demographics.xlsx")
```

```
# Creation of LONG database ----
```

```
db_long<-data.frame(
  RDMNUM=as.numeric(),
  is_crb=as.logical(),
  is_pp=as.logical(),
  visit=as.numeric()
)
db_names<-data.frame(
  short=c(
    "WABAQ","NIHSST",
    "dWABAQ","dNIHSST",
    "BIT","MRS",
    # AE stuff starts at 7
    "AE_total","SAE_total",
    "AE_neurological","AE_psychiatric","AE_cardiovascular",
    "AE_renal","AE_hematological","AE_gastrointestinal",
    "AE_metabolic","AE_respiratory","AE_immune.related.AE",
    "AE_ENT","AE_ophthalmic","AE_osteoarticular"
  ),
  long=c(
    "WAB Aphasia Quotient",
    "NIHSS",
    "WAB Aphasia Quotient differential",
    "NIHSS differential",
    "Barthel Index","Modified Rankin Scale",
    "Adverse events","Serious adverse events",
    "Neurological AEs","Psychiatric AEs","Cardiovascular AEs",
    "Renal AEs","Hematological AEs","Gastrointestinal AEs",
    "Metabolic AEs","Respiratory AEs","Immune-related AEs",
    "ENT AEs","Ophthalmic AEs","Osteoarticular AEs"
  )
)
for(score_to_diff in c("WABAQ","NIHSST"))
  for(i in 2:4)
    db_scores[,paste0("d",score_to_diff,"_",i)]<-db_scores[,paste0(score_to_diff,"_",i)]-
db_scores[,paste0(score_to_diff,"_1")]
for(pati in 1:nrow(db_scores))
  for(visi in 1:4){
    j=nrow(db_long)+1
    db_long[j,"RDMNUM"]<-db_scores[pati,"RDMNUM"]
    db_long[j,"is_crb"]<-db_scores[pati,"is_crb"]
    db_long[j,"is_pp"]<-db_scores[pati,"is_pp"]
    db_long[j,"visit"]<-visi
```

for(i in 1:2) # i represents the score that I transform to long format, and WAB and NIHSS have 4 visits so they are treated separately

```

  db_long[j,db_names$short[i]]<-db_scores[pati,paste0(db_names$short[i],"_",visi)]
  if(visi>1) for(i in 3:6)
    db_long[j,db_names$short[i]]<-db_scores[pati,paste0(db_names$short[i],"_",visi)]
}
# A function that generates a boxplot graph ----
# DFL should have the following; they should be in this order, not necessarily this names
# RDMNUM as whatever
# is_crb as logical
# visit as numeric
# value as numeric
graph_them_all<-function(dfl,ylb,ttl){
  names(dfl)<-c("RDMNUM","is_crb","visit","value")
  dfl$visit<-factor(dfl$visit)
  n<-table(dfl$is_crb)/sum(table(dfl$RDMNUM,dfl$is_crb)[1,])
  dfl$is_crb<-factor(dfl$is_crb,levels=c(F,T),labels=c(
    paste0("Placebo\n(N=",n[1],")"),
    paste0("Cerebrolysin\n(N=",n[2],")")))
  g<-
    ggplot(dfl,aes(x=factor(visit,levels=1:4),y=value,fill=is_crb))+
    geom_boxplot(outlier.size = 3,lwd=1)+
    stat_summary(fun=mean,position = position_jitterdodge(jitter.width = 0,jitter.height =
0),size=1,shape=5,show.legend = F) +
    stat_summary(fun.data=mean_sdl,fun.args = list(mult=1),geom="errorbar",position =
position_jitterdodge(jitter.width = 0,jitter.height =
0),linewidth=0.5,linetype="dashed",width=0.5,show.legend = F)+
    scale_fill_manual(values=c("#6495ED","#ee82ee"))+
    labs(title=ttl,x="Visit",y=ylb,fill="Treatment")+
    theme_light()+
    theme(plot.title=element_text(hjust=0),plot.subtitle = element_text(hjust=0),text =
element_text(size = 25))
  return(g)
}

```

# A function that generates a table ----

# the following rows:

```

# N (number of valid data points)    1
# mean-sd of group                   2
# median of group                    3
# p value diff inside group (paired) 4
# statistical test                    5

```

# the following columns:

```

# visit (2/3/4)                      1
# sub                                 2

```

```
# crb          3
# plc          4
# difference between them (unpaired) 5
# already_diff should be true for WAB and NIHSS, because they are already differentials
#             false for mRS and BI, because then I will manually compute diff 3-2 4-2
table_them_all<-function(dfl,already_diff){
  ret<-data.frame(
    visit=as.character(),
    sub=as.character(),
    crb=as.character(),
    plc=as.character(),
    diff_between_grps=as.character()
  )
  names(dfl)<-c("RDMNUM","is_crb","visit","value")
  ret[1:15,2]<-c("Number of valid data points N","Mean+SD of group","Median of group","p value
(differential)","Statistical test")
  for(visi in 2:4){
    ret[(visi-2)*5+1,1]<-visi
    vc<-dfl[dfl$is_crb&dfl$visit==visi,4]
    vp<-dfl[(!dfl$is_crb)&dfl$visit==visi,4]
    vc<-vc[!is.na(vc)]
    vp<-vp[!is.na(vp)]
    ret[(visi-2)*5+1,3]<-length(vc)
    ret[(visi-2)*5+1,4]<-length(vp)
    ret[(visi-2)*5+2,3]<-descr.numeric.meansd(vc)
    ret[(visi-2)*5+2,4]<-descr.numeric.meansd(vp)
    ret[(visi-2)*5+3,3]<-descr.numeric.median(vc)
    ret[(visi-2)*5+3,4]<-descr.numeric.median(vp)
    if(already_diff)
    {
      tvc<-test.numeric.paired.1(vc)
      tvp<-test.numeric.paired.1(vp)
      ret[(visi-2)*5+4,3]<-beautiful.p.value(tvc$p.value)
      ret[(visi-2)*5+4,4]<-beautiful.p.value(tvp$p.value)
      ret[(visi-2)*5+5,3]<-tvc$final.test
      ret[(visi-2)*5+5,4]<-tvp$final.test
    }
  }else if(visi!=2){
    vc<-dfl[dfl$is_crb&dfl$visit==visi,4]-dfl[dfl$is_crb&dfl$visit==2,4]
    vp<-dfl[(!dfl$is_crb)&dfl$visit==visi,4]-dfl[(!dfl$is_crb)&dfl$visit==2,4]
    vc<-vc[!is.na(vc)]
    vp<-vp[!is.na(vp)]
    tvc<-test.numeric.paired.1(vc)
    tvp<-test.numeric.paired.1(vp)
  }
```

```

    ret[(visi-2)*5+4,3]<-beautiful.p.value(tvc$p.value)
    ret[(visi-2)*5+4,4]<-beautiful.p.value(tvp$p.value)
    ret[(visi-2)*5+5,3]<-tvc$final.test
    ret[(visi-2)*5+5,4]<-tvp$final.test
  }
  tv<-test.numeric.unpaired(vc,vp)
  ret[(visi-2)*5+4,5]<-beautiful.p.value(tv$p.value)
  ret[(visi-2)*5+5,5]<-(tv$final.test)
}
for(i in 1:nrow(ret))
  for(j in 1:ncol(ret))
    if(is.na(ret[i,j]))ret[i,j]<-""
return(ret)
}

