## Coding systems utilized

The original database uses the following variables which are of interest for the data analysis. In the following list, unless otherwise noted, x represents the moment of measurement (1=baseline, 4=last visit at 90 days after treatment). Note that for Barthel Index and modified Rankin Scale, only scores at visits 2, 3, and 4 (30, 60 and 90 days after baseline, respectively) are available, with no value at baseline.

- RDMNUM = randomization number (unique to each participant)
- 
- Western Aphasia Battery
  - WABAQ\_x = Aphasia Quotient (0-100%)
- NIH Stroke Scale (Score)
  - NIHSST\_x = total score (0-42)
- Barthel Index
  - BIT\_x = total score (0-100)
- Modified Rankin Scale

- MRS\_x = total score (0-6 where 0=no symptom and 6=dead)

AEs and SAEs were stored in a separate database, from which we will retrieve the following information:

- Randomization number
- Whether the AE represents a SAE or not
- Based on the nature of the AE, some will be further classified by a clinician as being of the following nature:
  - Neurological
  - Psychiatric
  - Cardiovascular
  - Renal
  - Hematological
  - Gastrointestinal
  - Metabolic
  - Respiratory
  - Immune-related
  - ENT
  - Ophthalmic

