### Secondary objectives

The secondary objectives of the ESCAS study include the following:

- To assess the efficacy of Cerebrolysin and speech therapy versus placebo (saline solution) and speech therapy at 30, 60, and 90 days after baseline using measures of motor, neurological, and global functional outcome. These outcomes will be evaluated using the National Institutes of Health Stroke Scale (NIHSS), Barthel Index (BI), and modified Rankin Scale (mRS) scores at each time point.
- To evaluate the safety of Cerebrolysin and speech therapy versus placebo (saline solution) and speech therapy at 30, 60, and 90 days after baseline. Safety will be assessed by comparing the incidence of adverse events (AEs) and severe adverse events (SAEs) between the two treatment groups.
  - Additionally, we will measure specifically neurological, psychiatric, cardiovascular, renal, hematological, gastrointestinal, metabolic, respiratory, immune-related, ENT, ophthalmic and osteoarticular related adverse events.

The secondary outcome measures include changes in NIHSS, BI, and mRS scores from baseline to each follow-up time point (30, 60, and 90 days), as well as the incidence of AEs and SAEs.

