### Efficacy

- Comparison of the National Institutes of Health Stroke Scale (NIHSS) scores between the Cerebrolysin and placebo groups at each time point (30, 60, and 90 days after study inclusion) compared to baseline. The NIHSS is a widely used tool for assessing stroke severity and neurological deficits. Paired-measurement statistical tests will be used to analyze the NIHSS scores for each time point compared to baseline, in each group. Unpaired-measurement statistical tests will be used to determine the differences between efficacy of the treatment between groups, at each time point.
- Comparison of the modified Rankin Scale (mRS) scores between the Cerebrolysin and placebo groups at each follow-up time point (30, 60, and 90 days after study inclusion), as well as comparisons between the scores at 3rd and 4th visits compared to 2nd visit. The mRS is a commonly used measure of global disability and functional outcome in stroke patients.
- Comparison of the Barthel Index (BI) scores between the Cerebrolysin and placebo groups at each follow-up time point (30, 60, and 90 days after study inclusion), as well as comparisons between the scores at 3rd and 4th visits compared to 2nd visit. The BI is a measure of functional independence in activities of daily living.

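### For mRS and Barthel Index, the code tests day-60 and day-90 arm differences only as change from day 30, so the score comparisons listed under Efficacy are never tested at those visits

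*SAP*

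**What the plan says.** The Efficacy list under Secondary endpoints makes two commitments for each functional scale. The first is a between-arm comparison of scores at days 30, 60 and 90: "Comparison of the modified Rankin Scale (mRS) scores between the Cerebrolysin and placebo groups at each follow-up time point" and "Comparison of the Barthel Index (BI) scores between the Cerebrolysin and placebo groups at each follow-up time point". The second is added to it: "as well as comparisons between the scores at 3rd and 4th visits compared to 2nd visit".

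Later parts of the SAP are narrower or unclear:

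- Planned tables describes the BI and mRS tables as showing scores at visits 2/3/4, with "comparisons of differentials from visits 3/4 against visit 2, and comparisons of those differentials between groups, at visits 3/4".
- Exploratory statistics has visits 3 and 4 assessed against visit 2 with paired tests and the groups compared with unpaired tests. It does not say whether the unpaired tests use scores or changes.
- In the R source code, the ITT and PP loops both call `table_them_all` with `already_diff = F` for BI and mRS. At visits 3 and 4 this runs "vc<-dfl[dfl$is_crb&dfl$visit==visi,4]-dfl[dfl$is_crb&dfl$visit==2,4" and the matching line for placebo.

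Both statements of the secondary objectives use a third definition: "The secondary outcome measures include changes in NIHSS, BI, and mRS scores from baseline to each follow-up time point". Coding systems utilized rules that out for BI and mRS: "only scores at visits 2, 3, and 4 (30, 60 and 90 days after baseline, respectively) are available, with no value at baseline".

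**The concern.** The earliest BI and mRS values are from day 30, a post-randomisation visit. Treatment schedule puts cycle 1 on study days 1 to 14, before visit 2. The visit 2 window (day 30 ± 3, so days 27 to 33) can also run past the start of cycle 2 on day 29. Subtracting the day-30 score removes whatever arm difference has already developed.

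If that subtraction is the only thing tested at days 60 and 90, the analysis answers whether the arms diverged further after day 30. The comparison listed first under Efficacy asks whether function differs between arms at days 60 and 90. The two answers can differ sharply, and only the first would have a p-value.

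**Working it through.** **Code trace, `already_diff = F`.** For each visit, `vc` and `vp` start as the visit's scores in the Cerebrolysin and placebo arms. N, mean ± SD and median are written from these. Then:

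| Visit | `vc`, `vp` when the unpaired test runs | Listed under Efficacy |
|---|---|---|
| 2 (day 30) | scores | scores |
| 3 (day 60) | visit 3 minus visit 2 | scores, and comparison with visit 2 |
| 4 (day 90) | visit 4 minus visit 2 | scores, and comparison with visit 2 |

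The function has one between-arm test, `test.numeric.unpaired(vc,vp)`, and it comes after the overwrite. No other code tests BI or mRS between arms. This holds for ITT and PP.

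**Two side effects on the table.** The row label `p value (differential)` fits visits 3 and 4 but not the visit 2 between-arm entry, which tests scores. The printed N counts available scores, while the tests at visits 3 and 4 need pairs with visit 2. The number tested can be smaller, even in PP, whose definition does not require BI and mRS at visit 2.

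**Size. Inputs.** 60 per arm and d = 0.5 come from the sample size section; two-sided 0.05 comes from Statistical analysis. The SAP gives no BI or mRS effect or visit correlation, so the effect patterns and a correlation ρ of 0.5 to 0.85 are assumptions.

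**Formula.** Rank-sum power by noncentral t with effective n = n × 3/π. As a check, the SAP's 53 per group is reproduced by this formula one-sided (80.3%). A two-sided test would need 67. That is a separate matter and nothing here rests on it.

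*Scores at day 90.* Effective n = 60 × 0.955 = 57.3. Noncentrality = 0.5 × √(57.3/2) = 2.68. Power is 76%.

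*Coded change.* With unit SD at each visit, SD of change = √(2(1 − ρ)), which is 1.00, 0.775 and 0.548 at ρ = 0.5, 0.7 and 0.85. Standardised effect = (day-90 effect − day-30 effect) / SD of change.

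| Effect in SD, day 30 → day 90 | ρ | Standardised change effect | Power, coded change | Power, day-90 scores |
|---|---|---|---|---|
| 0.5 → 0.5 | any | 0 | 5% | 76% |
| 0.3 → 0.5 | 0.5 | 0.20 | 19% | 76% |
| 0.3 → 0.5 | 0.7 | 0.26 | 28% | 76% |
| 0.3 → 0.5 | 0.85 | 0.37 | 49% | 76% |
| 0.2 → 0.5 | 0.5 | 0.30 | 36% | 76% |
| 0.2 → 0.5 | 0.7 | 0.39 | 54% | 76% |
| 0.2 → 0.5 | 0.85 | 0.55 | 83% | 76% |

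**Simulation check.** Rank-sum simulation (4,000 trials per scenario) gave 74–76% on scores. On change it gave 4–5% for the constant effect, and at ρ = 0.7 and 0.85 it gave 27% and 48% (0.3 → 0.5) and 53% and 81% (0.2 → 0.5). A further simulation gave 46% where the table shows 49%. Running the code's own test-selection rule on a 7-level score with a constant 0.5 SD effect (2,000 runs, ρ from 0.5 to 0.9) gave 73–75% on scores and 4–6% on change.

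**The case against.** Much can be said for the plan, and several stronger readings do not hold.

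- **The comparisons are not wholly absent.** N, mean ± SD, median and boxplots of the scores at days 60 and 90 are produced by arm, and day-30 scores are tested. A reader might infer that a sustained early benefit would be invisible. It could show in the day-30 test and in the later descriptive figures. What is missing is any between-arm test of the later scores. The BI and mRS entries name no test, whereas the NIHSS entry does. But Exploratory statistics does provide unpaired tests for these scales, so a test of the listed comparisons is the natural reading.
- **The change contrast is itself planned.** Efficacy and Planned tables both include it, and the SAP never calls day 30 a baseline for these scales. The fault is that it replaces the score comparison at days 60 and 90.
- **The table is not plainly mislabelled.** A reader might infer that the day-60 and day-90 p-values will be taken for tests of the means above them. The row says it is a differential, which is right at visits 3 and 4. What stands is the wrong label at visit 2, and score summaries printed over a change test with no change summary or pair count.
- **A narrowing benefit gives no false result.** If the effect falls from 0.5 to 0.3 SD, the coded test points against the arm that is still better, rejecting in 16–69% of simulated runs (ρ 0.5 to 0.9). One might call that spurious, but the change after day 30 really does favour the other arm. The problem is having no score test beside it.
- **The normality pretest on mRS matters little.** It departs from Statistical analysis, which assigns Wilcoxon tests to ordinal values. On simulated 7-level scores, Shapiro-Wilk rejected in practically every run, so the code reaches Wilcoxon anyway.
- **The effect sizes are assumed.** The constant-effect case is the extreme. With most benefit after day 30 and ρ = 0.85, the coded contrast has the higher power.

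**Conclusion.** The SAP contradicts itself: Efficacy lists score comparisons at three visits, while Planned tables and the code test scores at one. Run as written, the code leaves the day-60 and day-90 score comparisons of both scales untested, in ITT and in PP. That follows from the text and code without any assumption.

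The loss of power depends on the time course of the effect, about which the SAP is silent. Against about 76% on day-90 scores, the coded change has 5% for a constant 0.5 SD effect, about 19–49% for 0.3 growing to 0.5 SD, and about 36–83% for 0.2 growing to 0.5 SD (60 per arm, ρ 0.5 to 0.85). The 5% needs no correlation assumption, because the expected contrast is 0.5 − 0.5 = 0.

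This should be fixed, but it does not undermine the trial. These are secondary endpoints in a trial that calls itself exploratory and plans no confirmatory analysis, and the primary Western Aphasia Battery analysis, which has a true baseline, is unaffected.

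**What to change.** 1. In `table_them_all` with `already_diff = F`, run the between-arm test on `vc` and `vp` at visits 2, 3 and 4 before they are overwritten. For mRS, call the rank-sum test directly, as Statistical analysis states for ordinal values.
2. Keep the change-from-visit-2 tests, which Efficacy plans, in separate rows labelled as change, with their own N, mean ± SD and median.
3. Label the visit 2 between-arm p-value as a test of scores.
4. Align Exploratory statistics and Planned tables with Efficacy, stating which quantity each unpaired test uses.
5. In both statements of the secondary objectives, replace change from baseline for BI and mRS with scores at each follow-up visit, because no baseline value exists.

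The cost is a few lines of code, some wording and eight more p-values (2 scales × 2 visits × 2 analysis sets). No new data are needed. It should be done before unblinding: the Source code section prefers no code changes afterwards, and choosing between scores and change with the results in view would be the data-driven decision the SAP sets out to avoid.
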